## 6.7

### Study Intervention after the End of the Study

After a participant with hepatic impairment has completed the study or has withdrawn early, the pre-study treatment will be continued, if required, in accordance with generally accepted medical practice. In the healthy participants, no further treatment or medical care is planned or required after the end of the study.

## 7

### Discontinuation of Study Intervention and Participant Discontinuation/Withdrawal

#### 7.1

#### Discontinuation of Study Intervention

Not applicable since evobrutinib is administered only once in the study.

#### 7.2

#### Participant Discontinuation/Withdrawal from the Study

- A participant may withdraw from the study at any time, at his/her own request or may be withdrawn at any time at the discretion of the Investigator for safety, behavioral, compliance, or administrative reasons.
- At the time of discontinuing from the study, if possible, a discontinuation visit will be conducted, as listed in the Schedule of Activities (SoA). The SoA specifies the data to collect at study discontinuation and follow-up, and any additional evaluations that need to be completed.
- If the participant withdraws consent for future involvement in the study, any data collected up to that point may still be used, but no future data can be generated, and any biological samples collected will be destroyed.

- A participant has the right at any time to request destruction of any biological samples taken. The investigator will document this in the site study records.

In case a participant must be withdrawn from the study, the Medical Monitor and clinical study leader for the Sponsor will be informed immediately.

If there is a medical reason for the withdrawal, appropriate medical care will be provided.

Participants who withdraw from the study prior to the first administration of study intervention or for any reason do not have a full PK dataset may be replaced. A discussion should occur between the Investigator and the Sponsor regarding whether a replacement may be considered.

### 7.3 Lost to Follow-Up

A participant will be considered lost to follow-up if he or she repeatedly fails to return for scheduled visits and is unable to be contacted by the study site.

The following actions will be taken if a participant fails to return to the clinic for a required study visit:

- The site will attempt to contact the participant and reschedule the missed visit as soon as possible, counsel the participant on the importance of maintaining the assigned visit schedule and ascertain if the participant wants to or should continue in the study.
- Before a participant is deemed “lost to follow-up”, the Investigator or designee will make every effort to regain contact with the participant: 1) where possible, make 3 telephone calls; 2) if necessary, send a certified letter (or an equivalent local method) to the participant’s last known mailing address, and 3) if a participant has given the appropriate consent, contact the participant’s general practitioner for information. These contact attempts will be documented in the participant’s medical record.
- If the participant continues to be unreachable, he/she will be deemed “lost to follow-up”.

## 8 Study Assessments and Procedures

- Study assessments and procedures and their timing are summarized in the SoA (Section 1.3).
- **No** protocol waivers or exemptions are allowed.
- Immediate safety concerns are discussed with the Sponsor immediately upon occurrence or awareness to determine if the participant should continue or discontinue study intervention.
- Adherence to the study design requirements, including those specified in the SoA, is essential and required for study conduct.
- All screening evaluations will be completed and reviewed to confirm that potential participants meet all eligibility criteria. The Investigator will maintain a screening log to record details of all participants screened, to confirm eligibility, and if applicable, record reasons for screening failure.

- Prior to performing any study assessments that are not part of the participant's routine medical care, the Investigator will obtain written informed consent as specified in [Appendix 2](#).
- Procedures conducted as part of the participant's routine medical care (e.g., blood count) and obtained before signing of the ICF may be used for screening or baseline purposes provided the procedures met the protocol-specified criteria and were performed within the time frame defined in the SoA (Section 1.3).
- A maximum of 200 mL of blood will be collected in any one-month period from each participant in the study, including any extra assessments that may be required.

## 8.1 Efficacy Assessments and Procedures

Not applicable.

## 8.2 Safety Assessments and Procedures

The safety profile of the study intervention will be assessed through the recording, reporting and analysis of baseline medical conditions, AEs, physical examination findings, vital signs, and laboratory tests.

Comprehensive assessment of any potential toxicity experienced by each participant will be conducted starting when the participants give informed consent and throughout the study. The Investigator will report any AEs, whether observed by the Investigator or reported by the participant; the reporting period is specified in Section [8.3.1](#).

### 8.2.1 Physical Examinations

- A complete physical examination will include, at a minimum, assessments of the Cardiovascular, Respiratory, Gastrointestinal and Neurological systems.
- A brief physical examination will include, at a minimum, assessments of the skin, lungs, cardiovascular system, and abdomen (liver and spleen).
- Investigators will pay special attention to clinical signs related to previous serious illnesses.
- Any physical examination abnormality findings which are clinically significant, before the ICF is signed, will be captured on the eCRF. After the ICF is signed, new physical exam abnormality findings will be captured on the AE form.

### 8.2.2 Vital Signs

- Height and weight will be measured at Screening and recorded.
- Tympanic temperature, pulse rate, respiratory rate, and blood pressure will be assessed.
- Blood pressure and pulse measurements will be assessed in a semi-supine position with a completely automated device. Manual techniques will be used only if an automated device is not available.

- Blood pressure and pulse measurements will be preceded by at least 5 minutes of rest for the participant in a quiet setting without distractions (e.g., television, cell phones).
- Vital signs (to be taken before blood collection for laboratory tests) will consist of 1 pulse and 3 blood pressure measurements (3 consecutive blood pressure readings will be recorded at intervals of at least 1 minute). The average of the 3 blood pressure readings will be recorded on the CRF.

### 8.2.3                    **Electrocardiograms**

- Single 12-lead ECG will be obtained as outlined in the SoA using an ECG machine that automatically calculates the heart rate and measures PR, QRS, QT, and QTc intervals. ECG assessments will be done after 5 minutes rest in supine position.

### 8.2.4                    **Clinical Safety Laboratory Assessments**

Blood samples will be collected in a fasted condition (after a fast of at least 8 hours).

- Blood and urine samples will be collected for the clinical laboratory tests listed in [Appendix 5](#) at the time points listed in the SoA. All samples will be clearly identified.
- Additional tests may be performed at any time during the study, as determined necessary by the Investigator or required by local regulations.
- The tests will be performed by the local laboratory.
- The Sponsor will receive a list of the local laboratory normal ranges before shipment of study intervention(s). Any changes to the ranges during the study will be forwarded to the Sponsor or designated organization.
- The Investigator will review each laboratory report, document this review, and record any clinically relevant changes occurring during the study in the AE section of the CRF. The laboratory reports will be filed with the source documents.
- Additional serum or highly sensitive urine pregnancy tests may be conducted, as determined necessary by the investigator or required by local regulation, to establish the absence of pregnancy at any time during the study.

### 8.2.5                    **Suicidal Ideation and Behavior Risk Monitoring**

Not applicable.

## 8.3                            **Adverse Events and Serious Adverse Events**

- The definitions of an AE and a Serious Adverse Event (SAE) are in [Appendix 4](#).
- The Investigator and any qualified designees (e.g., Sub-Investigators) are responsible for detecting, documenting, and recording events that meet the definition of an AE or SAE. The Investigator remains responsible for following up AEs that are serious or that caused the participant to discontinue the study, as specified in Section [8.3.3](#).

- Requests for follow-up will usually be made via the Study Monitor, although in exceptional circumstances the global patient safety department may contact the Investigator directly to obtain further information or to discuss the event.

### **8.3.1 Time Period and Frequency for Collecting Adverse Event and Serious Adverse Event Information**

- All SAEs will be collected from the signing of the ICF until the Follow-Up Visit/Discontinuation Visit at the time points specified in the SoA (Section 1.3). Beyond this reporting period, any new unsolicited SAEs that the Investigator spontaneously reports to the Sponsor will be collected and processed.
- All AEs will be collected from the signing of the ICF until Follow-Up Visit/Discontinuation Visit at the time points specified in the SoA.
- AEs/SAEs that begin before the start of study intervention but after obtaining ICF will be recorded on the Medical History/Current Medical Conditions CRF, not on the AE CRF.
- All SAEs will be recorded and reported to the Sponsor or designee immediately and under no circumstance will this exceed 24 hours, as indicated in [Appendix 4](#). The Investigator will submit any updated SAE data to the Sponsor within 24 hours of it being available using the same procedure that was used for the initial report.
- Investigators are not obligated to actively solicit AEs or SAEs after the end of study participation. However, if the investigator learns of any SAE, including a death, at any time after a participant has been discharged from the study, and he/she considers the event to be reasonably related to the study intervention or study participation, the Investigator will promptly notify the Sponsor.

### **8.3.2 Method of Detecting Adverse Events and Serious Adverse Events**

At each study visit, the participant will be queried on changes in his or her condition.

Care will be taken not to introduce bias when detecting AEs and/or SAEs. Open-ended and non-leading verbal questioning of the participant is the preferred method to inquire about AE occurrences.

The method of recording, evaluating, and assessing causality of AEs and SAEs and the procedures for completing and transmitting SAE reports are in [Appendix 4](#).

### **8.3.3 Follow-up of Adverse Events and Serious Adverse Events**

After the initial AE/SAE report, the Investigator is required to proactively follow each participant at subsequent visits/contacts. All SAEs will be followed until resolution, stabilization, the event is otherwise explained, or the participant is lost to follow-up (as defined in Section 7.3). Reasonable attempts to obtain this information will be made and documented. It is also the Investigator's

responsibility to ensure that any necessary additional therapeutic measures and follow-up procedures are performed. Further information on follow-up procedures is in [Appendix 4](#).

### 8.3.4 Regulatory Reporting Requirements for Serious Adverse Events

Prompt notification by the Investigator to the Sponsor of an SAE (particularly life-threatening and deaths) is essential so that legal obligations and ethical responsibilities towards the safety of participants and the safety of a study intervention under clinical investigation are met.

The Sponsor has a legal responsibility to notify both the local regulatory authority and other regulatory agencies about the safety of a study intervention under clinical investigation. The Sponsor will comply with country-specific regulatory requirements relating to safety reporting to the regulatory authority, Institutional Review Boards (IRB)/Independent Ethics Committees (IEC), and Investigators.

Individual Case Safety Reports will be prepared for suspected unexpected serious adverse reactions (SUSAR) according to local regulatory requirements and Sponsor policy and forwarded to Investigators, as necessary.

An Investigator who receives an Individual Case Safety Report describing a SUSAR or other specific safety information (e.g., Emerging Safety Issue Report, summary or listing of SAEs/SUSARs) from the Sponsor will review and then file it along with the Investigator Brochure in the Investigator's Site File and will notify the IRB/IEC, if appropriate according to local requirements.

### 8.3.5 Pregnancy

- Details of all pregnancies in female participants will be collected after the start of study intervention and until the end of the reporting period defined in Section [8.3.1](#).
- If a pregnancy is reported, the Investigator will inform the Sponsor within 24 hours of learning of the pregnancy and will follow the procedures specified below for collection of pregnancy information.
- Abnormal pregnancy outcomes (e.g., spontaneous abortion, fetal death, stillbirth, congenital anomalies, ectopic pregnancy) are considered SAEs.

#### Collection of Pregnancy Information

Female Participants who become pregnant

- The Investigator will collect pregnancy information on any female participant who becomes pregnant while she is in the study. The initial information will be recorded on the appropriate form and submitted to the Sponsor within 24 hours of learning of the pregnancy.
- The participant will be followed to determine the outcome of the pregnancy. The Investigator will collect follow-up information on the participant and the neonate, and the information will be forwarded to the Sponsor. Generally, follow-up will not be required for longer than 6 to

8 weeks beyond the estimated delivery date. Any termination of pregnancy will be reported, regardless of fetal status (presence or absence of anomalies) or indication for the procedure.

- While pregnancy itself is not considered to be an AE or SAE, any pregnancy complication or elective termination of a pregnancy for medical reasons will be reported as an AE or SAE.
- A spontaneous abortion (occurring at < 22 weeks gestational age) or stillbirth (occurring at >22 weeks gestational age) is always considered to be an SAE and will be reported as such.
- Any post-study pregnancy related SAE considered reasonably related to the study intervention by the Investigator will be reported to the Sponsor as specified in Section 8.3.4. While the Investigator is not obligated to actively seek this information in former study participants, he or she may learn of an SAE through spontaneous reporting.
- Any female participant who becomes pregnant while participating in the study will be withdrawn from the study.

## 8.4 Treatment of Overdose

For this study, any dose of evobrutinib greater than the maximum dose in the study within a 24-hour time period will be considered an overdose.

The Sponsor does not recommend specific treatment for an overdose.

Even if it not associated with an AE or a SAE, any overdose is recorded in the CRF and reported to global patient safety in an expedited manner. Overdoses are reported on a SAE and Overdose Report Form, following the procedure in [Appendix 4](#), the section on Reporting SAEs.

## 8.5 Pharmacokinetics

The following PK parameters will be calculated from the individual plasma concentration-time data, when appropriate:

| Symbol                                      | Definition   |
|---|--|
| AUC 0-tlast           | The area under the concentration-time curve (AUC) from time zero (= dosing time) to the last sampling time ( $t_{last}$ ) at which the concentration is at or above the lower limit of quantification. Calculated using the mixed log-linear trapezoidal rule (linear up, log down). |
| AUC 0-12 and AUC 0-24 | The area under the concentration-time curve (AUC) from time zero (= dosing time) to 12 or 24 hours at which the concentration is at or above the lower limit of quantification. Calculated using the mixed log-linear trapezoidal rule (linear up, log down).                        |
| AUC 0-∞                          | The AUC from time zero (dosing time) extrapolated to infinity, based on the predicted value for the concentration at $t_{last}$ , as estimated using the linear regression from $\lambda_z$ determination. $AUC_{0-∞} = AUC_{0-t_{last}} + C_{last\ pred} / \lambda_z$ .             |
| C max                            | Maximum observed concentration.  |
| t max                            | The time to reach the maximum observed concentration collected during a dosing interval (i.e., 1 st occurrence in case of multiple/identical C max values).  |
| t 1/2                            | Apparent terminal half-life. $t_{1/2} = \ln (2) / \lambda_z$ .   |

| Symbol               | Definition  |
|----------------------|---|
| CL/F                 | Apparent total plasma clearance after oral administration.
$CL/F = \text{Dose}_{\text{p.o.}} / \text{AUC}_{0-\infty}$ .  |
| Vz/F                 | Apparent volume of distribution during terminal phase after oral administration.
$V_z/F = \text{Dose} / (\text{AUC}_{0-\infty} * \lambda_z)$ following single dose.  |
| f u       | Free or unbound fraction of evobrutinib calculated as free concentration/total concentration (For each participant, 3 samples will be analysed to determine a percent of free fraction or unbound evobrutinib. The values from these samples if measurable will be used to estimate a mean percentage). |
| AUC 0-∞,u | Calculated as f u * AUC 0-∞   |
| C max, u  | Calculated as f u * C max   |
| CL u /F   | Calculated as Dose p.o. / AUC 0-∞,u   |

Whole blood samples of approximately 2 mL will be collected for measurement of plasma concentrations of evobrutinib. Collection times are specified in the SoA (Section 1.3). The actual date and time (24-hour clock time) of each sample will be recorded to calculate actual time elapsed since the prior dose administration. The sampling timing may be altered during the study based on newly available data (e.g., to obtain data closer to the time of peak plasma concentrations) to ensure appropriate monitoring.

The quantification of evobrutinib in plasma will be performed using a validated LC-MS/MS assay. Concentrations will be used to evaluate the PK of evobrutinib. The free fraction of evobrutinib sample will not be drawn separately but will be analyzed from the PK back up samples at 1.5, 4 and 12 hours.

Remaining samples collected for analyses of evobrutinib concentrations may also be used to evaluate safety or PD aspects related to concerns arising during or after the study. Full details of the bioanalytical methods will be described in a separate bioanalytical report.

Details on processes for collection and handling of these samples are in the Laboratory Manual. Retention time and possible analyses of samples after the End of Study are specified in the respective ICF.

PK parameters will be derived using noncompartmental methods with the validated computer program Phoenix® WinNonlin® (version 6.4 or higher; Certara, L.P., Princeton, New Jersey, USA).

The exact date/time of sample collection and drug administration (24-hour clock time) must be recorded in the eCRF and will be used in the calculation of PK parameters. The accepted time deviations from planned PK times that will not be considered a protocol violation are listed below:

[figure not shown]
| Procedure | Time Point (Relative Time) | Window Allowance |
|-----------|----------------------------|------------------|
| PK        | Predose                    | - 60 min         |
|           | 0.25 to 1 h postdose       | - 2 / + 2 min    |
|           | > 1 h to 12 h postdose     | - 5 / + 5 min    |
|           | > 12 h to 32 h postdose    | - 15 / + 15 min  |

The predose sample will be considered as if it had been taken simultaneously with the administration of study intervention.

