**Overall Design:**

This is an open-label, nonrandomized, parallel-group, single-center, single oral dose, Phase I study to investigate the PK and safety of evobrutinib in participants with different degrees of hepatic impairment compared to participants with normal hepatic function. Participants will be assigned to one of 3 groups: normal hepatic function (Group 1), mild hepatic impairment (Group 2), or moderate hepatic impairment (Group 3). Participants of Group 2 (8 participants with mild hepatic impairment) will be recruited in parallel with participants of Group 3 (8 participants with moderate hepatic impairment). After completion of enrollment of both Group 2 and Group 3, Group 1 consisting of 8 healthy participants will be recruited to match the group mean value to the participants of Group 2 and Group 3 regarding age ( $\pm 10$  years;  $\geq 18$  years old and  $\leq 79$  years old), and weight ( $\pm 10\%$ ;  $\geq 50$  kg and  $\leq 120$  kg). Efforts will also be made to have adequate sex representation in Group 1 (+ 2/- 2 male or female participants) that is similar to Groups 2 and 3. Up to 4 additional participants may be recruited in Group 1 for matching purpose.

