| Assessments & Procedures             | Screening
(Baseline
if Day -1
value not
available) | Study Day |   |   | Follow-Up/
Discontinuation | Notes   |
|--------------------------------------|--|-----------|---|---|-------------------------------|---|
| Study Day                            | -28 to -2  | -1        | 1 | 2 | 4 to 6                        | Day -1 value will be used as baseline if available. For ECG and vital sign, Day 1 predose value will be used as baseline. |
| Administration of Study Intervention |  |           | X |   |                               | Administration will occur 30 mins after starting a standard breakfast   |
| AE & SAE Review                      | X  | X         | X | X | X                             |   |
| Concomitant Medication Review        | X  | X         | X | X |                               |   |
| PK sampling                          |  |           | X | X |                               | Predose, 0.25, 0.5, 1.0, 1.5, 2.0, 3.0, 4.0, 6.0, 8.0, 10.0, 12.0, 16.0, 24.0, 32.0 hours postdose. See Section 8.5.      |
| PK sampling for free fraction        |  |           | X |   |                               | 1.5, 4, and 12 hours postdose. No separate blood collected. Backup samples will be used See Section 8.5                   |

Abbreviations: AE = Adverse event; ECG = Electrocardiogram; PK= Pharmacokinetics; SAE = Serious adverse event; WOCBP = woman of childbearing potential

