### 4 Study Design

#### 4.1 Overall Design

This is an open-label, nonrandomized, parallel-group, single-center, single oral dose, Phase I study to investigate the PK and safety of evobrutinib in participants with different degrees of hepatic impairment compared to participants with normal hepatic function.

Participants with hepatic impairment will be assigned to a group of mild (Child-Pugh class A) or moderate (Child-Pugh class B) hepatic impairment at Screening by use of the Child-Pugh system ([Table 1](#) and [Table 2](#)) and, in addition to participants with normal hepatic function, assigned to one of the following groups:

- Group 1: normal hepatic function
- Group 2: mild hepatic impairment
- Group 3: moderate hepatic impairment

Participants of Group 2 (8 participants with mild hepatic impairment) will be recruited in parallel with participants of Group 3 (8 participants with moderate hepatic impairment). After completion

of enrollment of both Group 2 and Group 3, Group 1 consisting of 8 healthy participants will be recruited to match the group mean value to the participants of Group 2 and Group 3 regarding age ( $\pm 10$  years;  $\geq 18$  years old and  $\leq 79$  years old), and weight ( $\pm 10\%$ ;  $\geq 50$  kg and  $\leq 120$  kg). Efforts will also be made to have adequate sex representation in Group 1 (+2/-2 male or female participants) that is similar to Groups 2 and 3. Up to 4 additional participants may be recruited in Group 1 for matching purpose.

**Table 1** Child-Pugh Grades/Class of Hepatic Impairment

| Child-Pugh Score | Child-Pugh Grade/Class | Severity of Hepatic Impairment |
|------------------|------------------------|--------------------------------|
| 5-6              | A                      | Mild                           |
| 7-9              | B                      | Moderate                       |
| 10-15            | C                      | Severe a            |

a Participants with severe hepatic impairment will not be included in this study.

**Table 2** Child-Pugh Criteria (FDA – Guidance for Industry, 2003)

|                                   | Points Scored for Observed Findings |            |          |
|-----------------------------------|-------------------------------------|------------|----------|
|                                   | 1                                   | 2          | 3        |

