Free (unbound) fraction will be calculated as free concentration/total concentration. For each participant, 3 samples will be analysed to determine a percent of free fraction (unbound) evobrutinib. The values from these samples, if measurable, will be used to calculate a mean free fraction, presented as percentage. The percentage free will be divided by 100% to calculate unbound PK parameters.

The parameters C_{max} , t_{last} , and t_{max} will be obtained directly from the concentration-time profiles. If C_{max} occurs at more than 1 timepoint, t_{max} will be assigned to the first occurrence of C_{max} .

Partial areas should be calculated using the nominal dosing interval. The actual dosing interval calculated from the CRF should not be used. However, actual times for partial AUC intervals may be used if the sample was taken within +/-10% of the protocol defined time, and the partial area would not be calculable using scheduled time.

The regression analysis should contain data from at least 3 different time points in the terminal phase consistent with the assessment of a straight line on the log-transformed scale. Phoenix WinNonlin “best fit” methodology will be used as standard. However, in some cases, further adjustment may be made by the pharmacokineticist, if warranted, after agreement with the Sponsor. The last quantifiable concentration should always be included in the regression analysis, while the concentration at t_{max} and any concentrations <LLOQ which occur after the last quantifiable data point should not be used.

If $\%AUC_{extra}>20\%$ and/or the coefficient of correlation (Rsq adj) of λ_z is <0.8 and/or the observation period over which the regression line is estimated is less than twofold the resulting $t_{1/2}$, the rate constants and all derived parameters (e.g. $t_{1/2}$, $AUC_{0-\infty}$, CL/f etc.) will be listed, flagged and included in the parameter outputs and may be excluded from the descriptive statistics. Any flags will be included in the study specific SDTM/ADaM and the exclusion of parameters agreed with the sponsor.

In the case that profiles have a measurable pre-dose concentration less than or equal to 5% of its C_{max} value, the participant’s data without any adjustments will be included in all PK measurements and calculations. If the pre-dose value is greater than 5% of the C_{max} , the participant will be dropped from all PK evaluations. However, this participant’s data will be flagged and reported.

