16.1.5.3 Primary Endpoint Analyses

Pharmacokinetic analyses will be done on the PK analysis population and according to the as-treated principle.

An analysis of variance (ANOVA) model including hepatic function group as a fixed effect will be applied to log-transformed PK parameters $AUC_{0-\infty}$, and C_{max} of evobrutinib of the hepatic impairment groups (Child-Pugh class A and Child-Pugh class B) and control group (Normal Hepatic Function). Separate models will be fitted for the comparison between the hepatic impairment groups (Child-Pugh class A and Child-Pugh class B) and the control group (Normal Hepatic Function). For each parameter, differences between the hepatic impairment groups and the control group will be estimated on the log scale (group mean ratio) together with corresponding 90% confidence intervals (CIs). The geometric least square means together with corresponding 95% CIs by hepatic function group will also be estimated. Point estimates and CIs will be back-transformed to the original scale.

The relationship between $AUC_{0-\infty}$ and C_{max} of evobrutinib and the hepatic function parameters (e.g., albumin-bilirubin score and De Ritis ratio as continuous variable) at baseline (arithmetic mean of screening and Day -1 values) will additionally be explored with a linear regression.

For secondary PK endpoints such as CL/f , $AUC_{0-\infty,u}$, $C_{max,u}$, and CL_u/f , the same ANOVA and linear regression analyses like for the primary endpoints will be performed.

17

References

Not applicable.

18 Appendices

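### Does the freedom to alter sampling times mid-study, with controls enrolled last, put the Cmax comparison at risk?

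*Protocol*

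**What the plan says.** Protocol 8.5 states that "The sampling timing may be altered during the study based on newly available data", with the example "to obtain data closer to the time of peak plasma concentrations". It sets no trigger or cut-off, and it does not require the three groups to stay on the same times.

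The enrolment order is fixed in Protocol 1.1 and 4.1: "After completion of enrollment of both Group 2 and Group 3, Group 1 consisting of 8 healthy participants will be recruited".

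Protocol 1.3 lists one set of times for everyone: "Predose, 0.25, 0.5, 1.0, 1.5, 2.0, 3.0, 4.0, 6.0, 8.0, 10.0, 12.0, 16.0, 24.0, 32.0 hours postdose".

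Protocol 8.5 defines Cmax as "Maximum observed concentration". SAP 16.1.4 says that it, with tmax and tlast, "will be obtained directly from the concentration-time profiles". For the comparison, SAP 16.1.5.3 says: "An analysis of variance (ANOVA) model including hepatic function group as a fixed effect will be applied to log-transformed PK parameters". Group is the only effect, as the code in SAP 18.1 confirms.

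**The concern.** An observed maximum depends on when one looks. If times near the peak were added after the impaired groups had finished, only the controls would have the denser grid. Their Cmax would rise and the impaired/normal ratio would fall, so the effect of impairment would be understated. An earlier change would still reach all controls but only some impaired participants. Moving a sample off the peak in controls would do the reverse.

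Such a shift is systematic: more participants would not average it out, the confidence interval would not show it, and the ANOVA would not correct it. The results are meant to inform dose-adjustment recommendations, and keeping one grid looks like a cheap safeguard.

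**Working it through.** **Inputs from the documents.** Half-life is 2 h in normal function and a predicted 6 h in moderate impairment, with the peak expected at 1.5 h (Protocol 4.2). The CV is 30 to 60% and each group has 8, with up to 4 extra controls (Protocol 1.1). The stated maximum reproduces: 3 × 8 + 4 = 28. The documents give no figure for a Cmax shift.

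**Assumptions.** One-compartment oral model; peak at 1.5 h, with 1.0 h also tried, and the same typical peak time in both groups; log-SD of peak time 0.3 or 0.5 and of elimination 0.3; independent lognormal residual noise of 0, 10 or 20%. The noise levels are not in the documents.

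**Step 1: change in control Cmax if only controls are on the new grid.**

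| Change | No noise | 10% noise | 20% noise |
|---|---|---|---|
| Add 1.25 h | +0.1 to +0.3% | +1.5 to +2.2% | +2.8 to +3.8% |
| Add 0.75, 1.25, 1.75, 2.5 h | +0.4 to +0.7% | +4.0 to +4.5% | +7.4 to +8.2% |
| Move 1.0 h to 2.5 h | −1.0 to −3.3% | −1.5 to −4.7% | −1.6 to −5.5% |

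The planned grid already has 0.5, 1.0, 1.5, 2.0 and 3.0 h around the peak. Finer sampling therefore recovers little, and most of the shift from added samples comes from taking the maximum of more noisy values. AUC from 0 to 32 h moves by 1.7% or less under these changes.

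**Step 2: scale against the interval.** The 90% CI factor is exp(± t × sqrt(ln(1 + CV²)) × sqrt(1/n1 + 1/n2)). At 8 versus 8, t = 1.761 on 14 df.

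- CV 30%: 1.761 × 0.2936 × 0.5 = 0.2585, so the ratio × 0.77 to 1.30.
- CV 60%: 1.761 × 0.5545 × 0.5 = 0.4883, so the ratio × 0.61 to 1.63.

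A 2% shift takes ln(1.02) = 0.0198, which is 8% of the log half-width at CV 30% and 4% at CV 60%. The extreme 8.2% shift takes ln(1.082) = 0.0788, or 30% and 16%. With 12 controls the factors are 0.79 to 1.26 and 0.65 to 1.55.

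**Step 3: net bias of the ratio against true Cmax.** A common grid is not unbiased. The flatter impaired profile has more samples near its maximum, so noise raises its observed Cmax more than that of the sharper control profile. The net bias is the common-grid bias divided by the control shift from step 1.

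| Grid in controls | 10% noise | 20% noise |
|---|---|---|
| Same as impaired | 1.017–1.025 | 1.032–1.046 |
| 1.25 h added | 0.998–1.007 | 0.998–1.015 |
| Four added | 0.976–0.984 | 0.955–0.973 |
| 1.0 h moved to 2.5 h | 1.033–1.076 | about 1.05–1.11 |

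The last cell is the quotient of the end values: 1.032 / 0.984 = 1.049 and 1.046 / 0.945 = 1.107. Without noise the common grid gives 1.002–1.004 and one added sample gives 1.000–1.003.

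One added sample brings the ratio nearer the truth than the common grid does. Four added samples reverse the sign at about the same size: at 10% noise, |ln 0.976| = 0.024 against ln 1.025 = 0.025.

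**The case for a change.** The strongest case for a change is that the permission is explicit and nothing else in the plan limits it. Adherence to the Schedule of Activities (Protocol 8) does not override a permission in the same protocol. Ethics approval of amendments (Appendix 2) governs process, not comparability between groups. SAP 16.1.3 deals with samples outside their windows, not with changed nominal times. A clause fixing the near-peak times would need no extra samples.

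All of that is right as a reading. It is also true that moving 1.0 h to 2.5 h in controls alone would add bias in the same direction as the common-grid bias. But that moves a sample away from the expected peak, whereas the clause gives the opposite as its example.

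For added samples, the case weakens at step 3. Restricting the compared Cmax to common times would discard valid observed maxima and would make the analysed Cmax differ from the one listed and summarised. In the model it gains no clear accuracy in return. The offset does depend on the assumed noise and on equal peak times, so it does not show that unequal grids are better. It shows only that the restriction cannot be counted on to help.

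**Conclusion.** No change to the plan is needed. The clause is an unused flexibility: no alteration is described, no formal interim analysis is planned (Protocol 9.4.4), and following the schedule as written gives one grid for all three groups.

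If near-peak samples were added in controls only, the shift in their Cmax would be under 1% without noise and about 1.5 to 8% under assumed noise of 10 to 20%. The study is descriptive (Protocol 9.1), and the shift lies well inside the confidence interval. It would offset the bias a common grid leaves, or replace it with one of similar size. Moving 1.0 h to 2.5 h would lower control Cmax by about 1 to 5.5%; this is the one case that clearly adds bias.

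Should times ever be altered, the actual times are recorded and a data review meeting precedes database lock. An analyst would report the change by group and show a common-time Cmax as a sensitivity analysis, identified in the study report as SAP section 4 requires for unplanned analyses. Cmax as defined in Protocol 8.5 should remain the primary measure. These sizes rest on the one-compartment model, the 2 h and 6 h half-lives, similar peak times in the groups, and noise levels that the documents do not give.
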